Disease processes and pain in osteoarthritis are known to have an impact on the patients' movement pattern, leading to dysfunctional habits with additional strain on the joint and other body parts¹⁷. Although physiotherapists observe and attend to the quality of patients' movement performance during exercise, correcting guidance is mainly focused on maintaining physiological joint angles or activating specified muscles¹⁸. From qualitative studies, it is well-known that patients with hip osteoarthritis, similar to other long-lasting pain conditions, experience changes in the way they perceive their body in movement and at rest^{19,20}. Their sensitivity to nuanced body perceptions may be disturbed and reduced by sensations of pain. Patients' way of coping with the disease is also influenced by how they interpret and act on bodily perceptions. For example is it likely that flares of increased pain is understood by patients as a sign for increased disease severity, and that they consequently develop negative beliefs and/or feelings of helplessness. The present study will investigate effects from Basic Body Awareness Therapy (BBAT), a movement learning program that aims to address patients movement habits based on enhanced movement awareness²¹. Revealing and utilizing own resources for movement under physiotherapy guidance is regarded to help patients understand and handle bodily signals in such a way that they develop functional movement patterns as well

as constructive ways of dealing with their disease. Hence, BBAT aims to address health aspects described in the bio-psycho-social model, based on the patients' active involvement, their movement experiences and their movement learning process^{22,23}.

Objectives and hypotheses

The purpose of this study is to examine the supplementary short- and long-term effects of BBAT in patients with hip OA, by comparing the outcomes (pain, functioning, and quality of life) of Patient Education (PE) alone with PE and BBAT combined. It is hypothesized that patients that participate in BBAT group therapy following PE show more short-term (4-5 months) and long-term (12-13 months) improvements compared to patients that participate in PE only.

Design and methods

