The trial is a single-centre, block-randomised, single-blinded, parallel-group trial conducted in collaboration between primary- and secondary health care in Bergen, Norway. It is a study of superiority, aimed to investigate whether PE followed by BBAT is more effective than PE alone.

Patients with verified (by x-rays and clinical symptoms) hip osteoarthritis referred to a 3,5 hours Patient Education (PE) course offered by Haukeland University Hospital, were invited to participate in the trial. *Inclusion criteria:* Women and men with primary OA according to the American College of Rheumatology Clinical Criteria ²⁴, living in Bergen or within a reasonable travelling distance (judged by the patients), commonly 1 hour. *Exclusion criteria:* Other known major physical or mental problems or disease that precludes movement training and participation in an educational program, known drug abuse, not speaking or understanding Norwegian language, pregnancy 5-9 months.

Between October 2015 and January 2019, 101 patients were enrolled. After given written informed consent to participate in the study, but before attending to the PE, the patients filled in questionnaires and were tested by a blinded assessor in accordance with the study protocol. Immediately after the PE course, they were randomized to one of two groups; A - intervention group, participating in 12 weekly sessions of BBAT, and B – comparison group, recommended to follow advice given in the PE course concerning self-training and/or guided physiotherapy in primary health care. A computer-generated block randomization schedule was used to allocate participants. A research coordinator not involved in the randomization procedure prepared opaque envelopes with allocation to groups and administered the distribution of envelopes immediately after each PE course.

Interventions

Patient Education was offered and led by an orthopaedic surgeon and an orthopaedic physiotherapist from Haukeland University Hospital, inspired by an educational program

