developed in Sweden and further developed for use in Norway (AktivA)²⁵. Emphasis was on describing the dynamic nature of joint structures and the importance of optimal loading, and giving advice on weight bearing and physical activity, adjusted to functional limitations and pain. Exercises addressing typical movement problems in hip osteoarthritis were demonstrated. Shock-absorbing materials in shoe soles were recommended, and weight reduction in overweight. Patients were advised to be physically active and to obtain guidance from physiotherapists in primary health care if needed. The patients' own experiences with hip osteoarthritis and sharing in the PE group were in the forefront.

Basic Body Awareness Therapy (BBAT) in groups was led by an experienced physiotherapist in primary care. Specific strategies promoting movement awareness and movement quality in daily life movements; lying, sitting, standing, relational and walking, were applied for the group as well as individually. The learning process in BBAT is illustrated as a cycle of seven steps; coming in contact with, exploring, experiencing, integrating, creating meaning of, mastering and conceptualizing movement aspects for more functional movement strategies²¹. Participants were to attend 12 weekly group sessions, each consisting of about 70 minutes of guided movements and 20 minutes of reflective talk in the group. Between the group sessions, patients were to practice movements regularly at home, and to implement experienced movement aspects into daily life activities and settings. They were to use a log-book for personal notes on movement experiences and reflections. As the PE course was organized once monthly, new patients were enrolled and joined the running BBAT group every month, meaning that the group consisted of new and old members at all times.

Data collection and outcomes

Electronic collection data is made through InfoPad, approved by the Data inspectorate. All participating patients were assessed according to the protocol described below at baseline and at 4-5 months' follow-up. The data collected are similar to those collected in the Norwegian osteoarthritis register (AktivA). The included tests are recommended by the Osteoarthritis Research Society International (OARSI) (40). Patients in the comparison group are asked to report any treatment or training activities that they have attended to during the intervention period.

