Intention-to-treat analysis of short-term follow-up data (4-5) months is performed during the fall 2019. To reduce the risk of bias during interpretation, blinded study results will be presented

to all authors. A researcher not involved with the study is asked to add A and B to the data sheet in line with the list of randomized participants, but without breaking the randomization code. Per protocol analysis of short-term data will be carried out after breaking the randomization code (spring 2020).

The long-term and final analyses of primary and secondary outcomes, as well as subgroup analyses related to cartilage thickness and additional treatment, will be conducted after data collection at 12-month follow-up is completed, the database is closed and the randomization code is broken (spring 2020).

Demographic data and characteristics of participants (e.g. age, height, weight, cartilage thickness, comorbidities, work status, type of work and medications) will be presented using descriptive statistics. Normality of continuous variables will be inspected visually on Q-Q plots. Mean and standard deviation will be used to describe normally distributed continuous variables, and median and upper and lower limits of the interquartile range to describe non-normally distributed continuous variables. Counts and percentages will be used to present categorical variables. No statistical testing will be performed to investigate differences in baseline characteristics between groups.

Differences between groups at both follow-up time points will be investigated separately using analysis of covariance (ANCOVA). Additionally, we will estimate a linear mixed effects model, including all time points, effect of treatment and their interaction.

In line with a patient-centred perspective, the clinical meaningful interpretation of change scores on the two primary outcomes, NRS Pain during walking and HOOS subscale ADL, will be discussed. A responder analysis will be conducted, based on values of minimal clinically important improvement (MCII) as anchors. No studies have, so far, calculated a MCII value for NRS Pain during walking or HOOS ADL in relation to physiotherapy. The values will therefore be defined as the mean change in scores in the category of patients who report to be “slightly improved” in pain and function on the PGIC⁴⁵. The proportions of responders in the intervention- versus control group will be analysed.

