The general significance level is set to 0.05. Using Bonferroni adjustment for 2 tests (2 primary outcomes; NRS and HOOS A), 0.025 is set as a marginal level. Residual plots will be used to check for normality assumptions and homoscedasticity. A per protocol analysis (PPA) will be used for sensitivity analysis for all outcomes. Subgroups related to cartilage thickness (0 versus > 0) will be investigated using a stratified ANCOVA as described above, if sufficient number of observations is available in both groups.

Missing data

Missing data will be investigated for any relations to the intervention or outcomes of interest (missing at random). Assuming the data missing at random, multiple imputation methods (MIM) will be used to generate random estimates, if necessary.

Missing items in patient reported questionnaires will be handled in accordance with guidelines for the questionnaire. If no guideline is available, mean imputation will be used if less than 10% of the items are missing.

Additional analyses

ANCOVA adjusted for concomitant treatments reported by participants will be conducted.

Harms

No adverse effects or risks of harm are documented from studies on PE or BBAT groups. If adverse events should occur, they will be categorized as treatment related or not, and treatment related events will be summarized and compared between groups.

Statistical software

IBM SPSS 24⁴⁶ and R⁴⁷ will be used for data handling and analyses.

References

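### Adjusting for, or splitting by, treatment most likely taken after randomisation does not estimate PE plus BBAT versus PE without assumptions that the SAP leaves unstated

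*SAP*

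**What the plan says.** The objective (Objectives and hypotheses) is "comparing the outcomes (pain, functioning, and quality of life) of Patient Education (PE) alone with PE and BBAT combined". On timing, Design and methods says: "Immediately after the PE course, they were randomized to one of two groups".

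Two places bring other treatment into the analysis:

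- Additional analyses: "ANCOVA adjusted for concomitant treatments reported by participants will be conducted".
- Statistical analysis plan, among the final analyses: "subgroup analyses related to cartilage thickness and additional treatment".

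Neither place defines the variable or dates it. For the cartilage item the SAP gives categories and a method: "Subgroups related to cartilage thickness (0 versus > 0) will be investigated using a stratified ANCOVA as described above". It gives no such sentence for additional treatment.

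The one place that describes how such information is gathered is Data collection and outcomes: "Patients in the comparison group are asked to report any treatment or training activities that they have attended to during the intervention period".

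Two statements bear on who takes other treatment. Group B is "recommended to follow advice given in the PE course concerning self-training and/or guided physiotherapy in primary health care" (Design and methods). The course content includes this: "Patients were advised to be physically active and to obtain guidance from physiotherapists in primary health care if needed" (Interventions).

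**The concern.** A covariate measured before randomisation can be adjusted for without changing what the group effect means. A covariate that arises afterwards can itself be a result of the allocation, or of how the patient is doing. Conditioning on it, in a model or by strata, then compares patients whom randomisation did not make alike.

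The SAP's own text makes both routes plausible. Self-training and physiotherapy are what group B is advised to pursue, so they belong to the comparator strategy. Physiotherapy is to be sought according to need, so uptake can follow symptoms.

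What is at stake is interpretation. A reader could take the adjusted or subgroup result as showing whether other treatment explains the BBAT result. It can show that only if, given arm and the model covariates, nothing else drives both uptake and outcome. The SAP neither states that assumption nor says what the group effect is meant to estimate.

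**Working it through.** **1. Timing.** Randomisation follows the PE course directly. The reports described in Data collection and outcomes cover the intervention period, which comes later. On this reading the variable arises after randomisation. Additional analyses gives no date, so this is the natural reading and not a certainty.

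**2. Inputs from the SAP (Sample size).** NRS on a 0-100 scale, difference 18, SD of change 30, 80% power, level 0.05, 44 per group, 15% drop-out. The planned figure reproduces: n = 2 × (1.960 + 0.842)² × (30/18)² = 43.6, so 44 per group. The point does not rest on this figure; it only supplies a scale.

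**3. The shift.** Let pA and pB be the shares reporting other treatment in the BBAT and comparison arms. Let D be the pooled within-arm mean difference, reporters minus non-reporters. With arm and this one binary covariate in a linear model,

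adjusted − unadjusted group effect (BBAT minus PE) = (pB − pA) × D.

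The SAP gives neither uptake nor D. **Assumption:** D between −18 and +18.

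| Uptake A / B (assumed) | Shift |
|---|---|
| equal | 0 |
| 40% / 50% | within ±0.1 × 18 = ±1.8 |
| 20% / 50% | within ±0.3 × 18 = ±5.4 |

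**4. Worked cases at 20% / 50%, direct BBAT effect −18 (all assumed).**

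- *Uptake follows symptoms; other treatment has no effect.* A latent symptom course has correlation 0.3 with outcome, and a patient reports treatment above 0.842 SD in arm A or 0 in arm B. D = 30 × 0.3 × (0.280 + 0.399)/(0.16 + 0.25) = 14.9, so the shift is 0.3 × 14.9 = +4.5. Randomised effect −18.0; adjusted −13.5. Reporters: −18 + 9 × (0.280/0.2 − 0.399/0.5) = −12.6. Non-reporters: −18 + 9 × (0.399/0.5 − 0.280/0.8) = −14.0.
- *Uptake unrelated to prognosis; other treatment lowers pain by 18.* Randomised effect −18 + 0.3 × 18 = −12.6; adjusted −18.0; shift −5.4. Here the adjusted model does recover the direct effect, because nothing confounds it.
- *Neither link present.* Shift 0.

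**5. A second set of assumptions.** A simulation of one million patients fixed the total effect at −18. Other treatment had effect 0 or −10, and unmeasured severity was worth 0, 10 or 15 points per SD (correlation 0.5 with latent uptake when present). The unadjusted contrast was −18.0 throughout. The adjusted contrast was −18.0 at 30% in both arms, −16.8 to −19.0 at 30% / 40% (A / B), and −14.3 to −21.0 at 20% / 50%.

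**6. Precision.** With 101 × 0.85 / 2 ≈ 43 per arm, SE = 30 × √(2/43) = 6.5 unadjusted. Adjusted at 20% / 50%, r² = 0.3²/(4 × 0.35 × 0.65) = 0.099 and SE = 6.47/√(1 − 0.099) = 6.8. If separate strata are analysed at that uptake, SE is 30 × √(1/8.6 + 1/21.5) = 12.1 for reporters and 30 × √(1/34.4 + 1/21.5) = 8.2 for non-reporters.

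**7. Who was asked.** Data collection and outcomes mentions the comparison group; Additional analyses speaks of participants. If arm A was not asked and is coded as none, the reporter stratum holds no arm A patients, and the adjusted coefficient becomes all of arm A against the non-reporting part of arm B. In the first case of step 4 that contrast would be −18 + 9 × 0.399/0.5 = −10.8.

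**The case against.** The SAP never says that this ANCOVA estimates the trial contrast. That task belongs to the ITT analysis, and the ANCOVA is a single sentence among additional analyses. This stands, and it limits the weight of the point. It does not remove it, because the heading does not tell a reader what the adjusted group effect means.

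The covariate could be treatments in use at baseline, since medications are listed among participant characteristics. Adjustment would then be harmless. The reading is possible but less natural, because the reported treatments that the SAP describes belong to the intervention period.

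Both arms heard the PE advice before randomisation, so unequal uptake is not documented. That is right, and at equal uptake the shift is zero. Group B is nevertheless specifically directed to that advice while group A attends BBAT, so a difference is plausible.

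A reader might infer that the additional-treatment subgroup is a separate analysis left without categories or method. The text does not settle this: the adjusted ANCOVA may be the method for that item. The stratum results and standard errors in the working apply only if separate strata are intended.

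A reader might also infer that nothing can be estimated because arm A was not asked. The SAP does not say that arm A was left out, and even then the model would return a coefficient. The difficulty would be its meaning.

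**Conclusion.** The point holds, and it is minor. On the natural reading, the concomitant-treatment ANCOVA and any subgroup by additional treatment condition on a variable that follows randomisation and can depend on arm and symptoms. Their group effects do not estimate PE plus BBAT versus PE unless no-confounding assumptions are added, and the SAP states none.

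The figures above show only that a shift is possible. They rest on assumed uptake and an assumed D, and the shift may be positive, negative or zero. A reader might infer that the trial's main result is biased by a known amount. The documents do not support that: the SAP does not name this covariate for the ITT ANCOVA or the mixed model, so both are unaffected, and it gives nothing from which to size a shift. The conclusion falls away if the covariate means treatments in use at baseline.

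**What to change.** Restrict covariate adjustment and effect subgroups to variables measured before randomisation, for example treatments in use at baseline. Report concomitant treatment descriptively by arm: type, number and share of patients.

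If the adjusted or subgroup analysis is kept:

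- define the variable (which treatments, which reporting window, which categories) and say whether the two mentions are one analysis;
- label it exploratory and state that it is not the randomised effect of PE plus BBAT versus PE;
- reconcile Data collection and outcomes with Additional analyses by stating which arms were asked, and compare arms only if both were asked the same question.

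If a direct effect is really wanted, name that estimand, its assumptions and a method suited to it.

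The cost is a change of SAP wording, with one supplementary result dropped or downgraded.

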^{26,27}, we assumed a between-participant standard deviation of change of 30 points. The required sample size, with 80% power and the significance level of 0.05 was 44 in each group. Allowing for a 15% drop-out, a total of 100 patients was required. Disability was assessed by the Hip disability and Osteoarthritis Outcome Score (HOOS). Referring to power calculation of a previous relevant study, 74 patients are needed to detect a clinically relevant change of 10 points on the subscale in patients with hip pain ($SD \pm 15$, power = 0.80 and $\alpha = 0.05$)¹⁵. A total of 100 patients were, accordingly, a sufficient sample size for both measures.

The intervention, BBAT, has been tried out in a pilot study showing promising results and has shown positive results in other patient groups⁴⁴. No adverse effects have been reported. Plans for interim analyses or stopping guidance were therefore not considered relevant.

Adherence and protocol deviations

Definition of adherence to the intervention and how this is assessed including extent of exposure

The physiotherapist leading the BBAT group kept a record over patient attendance. Patients that participate at least 10 times in BBAT groups are regarded to having completed the intervention. A table will show the number of BBAT group sessions attended to during the intervention period.

Definition of protocol deviations for the trial

No deviations from the original protocol.

Definition of analysis populations

All participants (n = 101) will be included in an intention to treat (ITT) analysis investigating the effectiveness of BBAT groups in clinical and practical settings; a real life situation. Patients who have completed the treatment (10 BBAT group sessions) and have been available for all baseline and 4-5 month follow-up measurements, are included in a per protocol analysis (PPA) investigating the maximum treatment efficacy in perfect compliers.

Withdrawal/follow-up

A flow-chart will be made to show the level of patient participation throughout the study, illustrating withdrawals/lost to follow-up data in both groups separately, with timing and reasons for withdrawal/lost to follow-up.

Statistical analysis plan

The present statistical analysis plan will be made publicly through registration in ClinicalTrials before any analysis is performed. The statistical analyses will be performed in close collaboration with an independent statistician who is unaware of group assignment.

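### The only between-arm harms analysis stated is of events judged treatment related, so it depends on an undefined attribution that may differ by arm

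*SAP*

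**What the plan says.** The Harms section of the SAP opens from an expectation of no harm: "No adverse effects or risks of harm are documented from studies on PE or BBAT groups". If events do occur, "they will be categorized as treatment related or not", and "treatment related events will be summarized and compared between groups". That is the whole harms analysis. No summary or comparison of all events, or of events judged unrelated, appears elsewhere in the SAP. The Sample size section makes a similar statement about earlier experience with BBAT, "No adverse effects have been reported", and uses it to explain why no interim analysis or stopping guidance is planned.

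The arms are described under Design and methods. Both attend the education course first: "Immediately after the PE course, they were randomized to one of two groups". They then differ. One is "A - intervention group, participating in 12 weekly sessions of BBAT"; the other is the "comparison group, recommended to follow advice given in the PE course concerning self-training and/or guided physiotherapy in primary health care". The same section calls the trial single-blinded and describes a blinded assessor for testing. The SAP does not say who judges relatedness, by what rule, with what knowledge of the arm, or which exposure counts as treatment.

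**The concern.** Relatedness is a judgement made after randomisation about a cause, and in this trial the possible causes differ by arm. The same pain flare could be put down to guided movement sessions in a BBAT patient and to the disease in a comparison patient. The share of events called related may then differ between arms even when the event rates do not.

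The error can go either way:

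- If events are attributed more readily in the BBAT arm, the comparison shows an excess that is not there.
- If few events are called related in either arm, a real difference in event rates can disappear from the only comparison stated.

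A comparison of all events by randomised arm has no attribution step. It keeps the protection of randomisation, provided events are collected in the same way in both arms.

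**Working it through.** The Harms section gives no event rate, attribution share, test or power, so there is no figure of the plan to reproduce. The calculation shows direction and possible size only.

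**Inputs from the SAP**
- 101 participants (Definition of analysis populations).
- General significance level 0.05 (Statistical analysis plan).

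**Assumptions, not in the SAP**
- Arm sizes of 51 (BBAT, A) and 50 (comparison, B).
- A two-sided Fisher exact test, as no test is named for harms.
- The same true proportion *r* of patients with an event in both arms, from 10% to 40%.
- A share *q* of those patients whose event is called related: 50% in A, and 0% to 50% in B.

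**Step 1: apparent difference with no true difference.** The related-event rate in an arm is *r* × *q*, so the spurious risk difference is *r* × (*q*A − *q*B). With *q*A = 0.50 and *q*B = 0.10:

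- *r* = 10%: 5% v 1%, a difference of 4 points
- *r* = 20%: 10% v 2%, 8 points
- *r* = 30%: 15% v 3%, 12 points
- *r* = 40%: 20% v 4%, 16 points

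**Step 2: how often this is declared significant.** Summing the binomial probabilities of all outcomes with Fisher p ≤ 0.05 gives:

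| Comparison | *r* = 10% | 20% | 30% | 40% |
|---|---|---|---|---|
| All events, by arm | 2.7% | 3.8% | 4.0% | 4.2% |
| Related, 50% v 50% | 1.4% | 2.7% | 3.4% | 3.8% |
| Related, 50% v 25% | 1.4% | 6.9% | 13.4% | 21.0% |
| Related, 50% v 10% | 2.6% | 20.2% | 42.1% | 61.5% |
| Related, 50% v 0% | 4.1% | 40.2% | 79.7% | 95.8% |

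The all-event row stays below 5% whatever the attribution. The related-event rows stay there only when attribution is equal or events are rare.

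**Step 3: the opposite error.** Let the true rates be 40% in A and 20% in B. Comparing all events detects this with 55% power. If 10% of events are called related in each arm, the compared rates are 0.40 × 0.10 = 4% and 0.20 × 0.10 = 2%, and power falls to 0.7%. Attribution is equal here; the loss comes from its being sparse.

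**The case against.** The strongest reply has four parts.

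**Treatment related is not BBAT related.** The Harms section names both the education course and BBAT as possible sources of harm. Comparison patients attend the course and may do self-training or physiotherapy, and under Data collection and outcomes they are asked to report such activity. A flare after that training could be called related. This stands. A reader might infer that the comparison arm's count is zero by construction, but the text does not support that. The 50% v 0% row above is an extreme, not the expected case. The harms comparison reflects event rates as well as attribution.

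**Nothing says the arm is known when relatedness is judged.** This also stands. A reader might infer unblinded attribution from the single-blind design, but the SAP is silent and the protocol, which is not shown, may settle it. What can be said is that the SAP describes no blinded judgement.

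**The SAP does not write the word only, and the rates are invented.** Every event is to be categorised, so the all-event count will be available. At a 10% event rate even 50% v 0% attribution gives a significant difference in only 4.1% of trials, and nothing in the SAP supports 20% to 40%. The size is therefore uncertain. The stated rule still compares one class of events and gives no analysis for the rest.

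**Other data bear on harm without attribution.** Walking pain and the HOOS subscales are compared by intention to treat, and withdrawals are shown by arm with reasons. These partly cover a worsening of pain or function, though they do not replace an event table.

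**Conclusion.** The point holds as a weakness in a stated analysis rule. The one between-arm harms comparison in the SAP rests on an attribution with no definition of treatment and no described blinding, in a design where only one arm receives BBAT. Following it can create or hide a difference.

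Under the main illustration (50% v 10% attribution, 51 v 50 patients, equal true rates of 10% to 40%), a false significant difference arises in about 3% to 62% of trials, against about 3% to 4% for all events. At the 10% event rate the two approaches are practically the same (2.6% v 2.7%), so the consequence is small if events are rare. All of this rests on assumed event rates, attribution shares, arm sizes and test. The advantage of the all-event comparison also depends on like collection in both arms.

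Two stronger conclusions might be drawn and are not supported. One is that the trial cannot support any safety statement. That is too absolute, given the assumed rates and the intention-to-treat comparison of pain and function. The other is that zero related events among 50 patients, with its one-sided 95% upper bound of 1 − 0.05^(1/50) = 5.8%, shows the defect. That bound is a limit of sample size; it applies equally to zero events of any kind, and the change below would not alter it.

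**What to change.** Replace the Harms rule so that the main analysis covers all adverse events and serious adverse events by randomised arm, regardless of attribution. Report the number of patients with at least one event, the number of events, and the risk difference with a 95% confidence interval. Use the same observation period and the same collection method in both arms, and say so in the SAP or by reference to the protocol.

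Keep treatment-related events as a descriptive breakdown. State which exposures count as treatment (the course, BBAT, or the comparison arm's own training) and who judges relatedness, preferably without knowledge of the arm.

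The cost is a few sentences and one extra table, built from events the plan already requires to be categorised. The downside is that the intervals will be wide if events are few.
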